7.2 Analysed data sets

The primary data set for analysis will contain all data collected in the Intent-to-treat population, which is defined as all subjects who received the investigational device and have at least one post-treatment assessment. Certain sensitivity analyses may be also done in the Per-protocol population, which is defined as all subjects who received the investigational device and have completed the investigation without major CIP deviations.

7.3 Missing data

Missing data will not be estimated and/or imputed in any way.

7.4 Methods of analysis

In general, collected data will be listed and descriptive statistics will be performed, with all repeating measurements being tabulated by the visit. For continuous variables, descriptive statistics will include the number of observations, minimum, maximum, mean and standard deviation, or median and interquartile range, as appropriate based on data distribution. For discrete variables, summary statistics will include the total number of observations, frequency and percentages.

Demographic data, use of additional anaesthetic, initial amount of the filler applied, and occurrence of the Touch-up treatment with the amount of the filler applied will be listed by subject and summarized

using descriptive statistics. Other data collected will be listed per subject and summarized as described in the SAP.

7.4.1 Performance endpoints

As two facial folds of each subject will be considered, there are two measurements per subject for NLF-SRS. No great differences between the folds are expected, thus the mean of both measurements will be used for analyses. Individual NLF-SRS grades per visit will be calculated as the mean of grades assigned to the left and the right nasolabial fold, respectively. The absolute NLF-SRS change versus baseline will be computed by subtracting the value obtained on Day 0 from that of the corresponding visit. Absolute NLF-SRS change from baseline will be summarized by the visit using descriptive statistics and additionally the 95% confidence intervals of the mean will be given. In addition, the proportion of the NLF-SRS change values ≥ 1 , or ≥ 2 , respectively, will be calculated.

Individual GAIS grades, subjects' satisfaction with aesthetic outcome, and pain ratings will be summarized and tabulated by visit using descriptive statistics.

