Primary performance endpoints	 The average change versus baseline (Day 0) in the NLF-SRS grade of nasolabial folds at Week 24 as evaluated by the investigator The proportion of subjects with the NLF-SRS grade reduced by ≥1 point versus baseline at Week 24
Secondary	• The average change versus baseline in the NLF-SRS grade at Week 4 and

performance endpoints	 Week 36 as evaluated by the investigator The proportion of subjects with the NLF-SRS grade reduced by ≥1 point versus baseline at Week 4 and Week 36 The proportion of subjects with aesthetic improvement at Week 4, Week 24 and Week 36, as evaluated by the investigator using the Global Aesthetic Improvement Scale (GAIS) Subjects' satisfaction with aesthetic outcome of the treatment at Week 4, Week 24, Week 24 and Week 36, as evaluated by the subject The average pain intensity during and after the treatment, as evaluated by the subject using an 11-point Numeric Pain Rating Scale (NPRS) immediately after the last injection and 15 min. thereafter, respectively The proportion of subjects with the NLF-SRS grade reduced by ≥1 point versus baseline at Week 24 as evaluated by the independent reviewer of photographs.
Safety endpoints	Occurrence and frequency of adverse events
Statistical methods	All analyses will be done in the Intent-to-treat population, defined as all subjects who received the investigational device and have at least one post-treatment assessment. Individual NLF-SRS grades per visit will be calculated as the mean of grades assigned to the left and the right nasolabial fold, respectively. The absolute NLF-SRS change versus baseline will be computed by subtracting the value obtained on Day 0, and summarized by the visit using descriptive statistics. Additionally, the 95% confidence intervals of the mean will be given and proportions of the NLF-SRS change values ≥ 1 or ≥ 2 , respectively, will be calculated. Adverse events will be summarised by preferred term and system organ class, and also by intensity, relationship to the investigational medical device or procedure, and seriousness.

Schedule of procedures and events

Table 1. Schedule of procedures and events

	VISIT 1	VISIT 2	VISIT 3	VISIT 4	VISIT 5
	Baseline Visit*	Week 2 Visit	Week 4 Visit	Week 24 Visit	Week 36 Visit
Visit window	Day 0	Week 2 (± 2 days)	Week 4 (± 4 days)	Week 24 (± 7 days)	Week 36 (± 7 days)
Informed consent	X**				
Demographic data ^a	X**				
Medical history	X**				
Prior medication ^b	X**				

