6.1.1 Primary performance endpoints

The performance of the investigational device will be evaluated using the following primary endpoints (justification is provided in Section 3.3):

- The average change versus baseline (Day 0) in the NLF-SRS grade of nasolabial folds at Week 24 as evaluated by the investigator.
- The proportion of subjects with the NLF-SRS grade reduced by ≥1 point versus baseline at Week 24

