Sample size calculation was performed by the sponsor. Up to 60 subjects with moderate to severe nasolabial folds will be enrolled in order to obtain the 24-week performance and safety data from at least 40 of them. If less than 60 subjects will be recruited at the point when at least 40 subjects complete the Week 24 assessment, a decision to continue the recruitment up to 60 subjects in total will be made by the sponsor. This sample size is arbitrarily selected and is considered appropriate for the post-market follow-up clinical investigation and sufficient to provide robust estimations on performance and safety parameters in the study population. With a sample size of 40 to 60, a two-sided 95% confidence interval for a single proportion using the large sample normal approximation will extend 0.076 to 0.093 from the observed proportion for an expected proportion of 0.900. Thus, a robust estimation of the success rate at week 24 can be derived.

Study and treatment duration

The duration of the clinical investigation will be 9 months for each participating subject. A single application of Princess® VOLUME Lidocaine, with optional Touch-up treatment after two weeks, if the desired level of correction has not been achieved with the initial application, is planned.

The total expected duration of the clinical investigation is about 13 months with an expected recruitment period of 3 to 4 months.

2 Performance and Safety Endpoints

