3.2 Intention-to-treat Population (ITT)

The intent-to-treat population (ITT) consists of all subjects who received the investigational device and had at least one post-treatment assessment (e.g., first pain assessment after injection).

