3.5 Assignment of Analysis Sets to Analysis

The ITT will be considered the primary analysis set. All performance and additional endpoint analyses are based on the ITT. All primary endpoint analyses will be also performed for the modITT and PP. All secondary or additional endpoint analyses will be also performed for the PP. All safety analyses will be based on the SAF.

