4.3.1 Analysis of Primary Performance Endpoints

The primary performance endpoints will be analyzed for the ITT, modITT and PP.

The change from baseline in the average grade of NLF-SRS as assessed by the investigator to Week 24 will be summarized with descriptive statistics for continuous variables. Additionally, the 95% confidence intervals of the mean will be given.

The proportion of subjects with the average grade of NLF-SRS as assessed by the investigator reduced by ≥1 point versus baseline will be summarized with frequency tables at Week 24.

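### Protocol 7.4.1 and the synopsis state the NLF-SRS responder rule with the wrong sign, and the SAP does not say which subjects form the Week 24 denominator

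*Protocol*

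**What the plan says.** **Endpoint.** The second primary endpoint in Protocol 6.1.1 is "The proportion of subjects with the NLF-SRS grade reduced by ≥1 point versus baseline at Week 24". SAP 2.1 repeats it. SAP 4.3.1 takes the proportion of subjects whose average grade is "reduced by ≥1 point versus baseline will be summarized with frequency tables at Week 24".

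**Protocol analysis rule.** Protocol 7.4.1 averages the left and right folds into one grade per subject per visit, and computes change as the visit value minus the Day 0 value. It then says that "the proportion of the NLF-SRS change values ≥ 1 , or ≥ 2 , respectively, will be calculated". The synopsis (Statistical methods) also subtracts the Day 0 value and says that "proportions of the NLF-SRS change values ≥ 1 or ≥ 2 , respectively, will be calculated". SAP 4.3 keeps the same subtraction.

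**Passages that bear on the denominator.**
- Protocol 7.3: "Missing data will not be estimated and/or imputed in any way". SAP 4.6 also rules out imputation.
- SAP, Number of subjects: the precision statement begins "With a sample size of 40 to 60, a two-sided 95% confidence interval for a single proportion" and gives half-widths of 0.076 to 0.093 at an expected proportion of 0.900. Forty is the minimum number of subjects from whom Week 24 data are sought; 60 is the enrolment ceiling.
- SAP 3.2 and 3.5: the ITT is the primary set. It admits any treated subject who "had at least one post-treatment assessment (e.g., first pain assessment after injection", so a Week 24 grade is not needed to enter it.
- SAP 4.8: the default table for qualitative variables has a row labelled *missing* above a total of 100.0.

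**The concern.** The two parts concern the same primary endpoint.

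First, the threshold in Protocol 7.4.1 and the synopsis has the opposite sign to the endpoint that it is meant to analyse. A programmer or reader who applied the protocol text literally would report the share of subjects who got worse.

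Second, the plan accepts Week 24 data from as few as 40 of up to 60 subjects but does not say what happens in the percentage to ITT subjects without a Week 24 grade. Its own provisions lean in different directions, and the estimate depends on the choice whenever grades are missing. The study is open label, so a denominator settled only when tables are programmed would be chosen with outcomes visible.

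**Working it through.** **1. The plan's own figure.** Half-width = 1.96 × √(p(1 − p)/n), with p = 0.900 (SAP, Number of subjects).
- n = 60: 1.96 × √(0.09/60) = 0.0759
- n = 40: 1.96 × √(0.09/40) = 0.0930

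These match the stated 0.076 and 0.093.

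**2. Sign.** Inputs: each fold is graded 2 or 3 at baseline (Protocol 6.3.4); the scale runs from 0 to 4 (Protocol 6.4.5); change = visit − Day 0 (Protocol 7.4.1).
- Lowest possible change: 0 − 3 = −3. Highest: 4 − 2 = +2. Every improvement is below zero.
- A change of at least 1 is therefore a worsening of at least 1 grade. A change of at least 2 is possible only if both folds go from 2 to 4.
- Illustration: 36 subjects with change −1 and 4 with change 0. Literal rule (change ≥ 1): 0/40 = 0%. Endpoint (change ≤ −1): 36/40 = 90.0%.

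**3. Denominator, from the text.**

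| Points to subjects with a Week 24 grade | Points to all ITT subjects |
|---|---|
| Precision based on n = 40 to 60, where 40 is the minimum with Week 24 data | ITT is primary, and one post-injection pain score is enough to enter it |
| No imputation (Protocol 7.3, SAP 4.6) | Default table has a *missing* row inside a total of 100.0 (SAP 4.8) |

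SAP 4.3.1 prescribes frequency tables and gives no denominator.

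**4. Denominator, in numbers.** Assumptions, none of them stated in the documents as a forecast: 60 treated and in the ITT; 90% response among those with a Week 24 grade; normal-approximation 95% intervals, as in the SAP.

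| Week 24 grades | Responders | Over graded subjects | Over all 60 | Gap (points) |
|---|---|---|---|---|
| 40 | 36 | 36/40 = 90.0% (80.7 to 99.3) | 36/60 = 60.0% (47.6 to 72.4) | 30.0 |
| 50 | 45 | 45/50 = 90.0% (81.7 to 98.3) | 45/60 = 75.0% (64.0 to 86.0) | 15.0 |
| 60 | 54 | 54/60 = 90.0% (82.4 to 97.6) | the same | 0 |

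Over all 60, the half-widths are 1.96 × √(0.60 × 0.40/60) = 0.124 with 40 grades and 1.96 × √(0.75 × 0.25/60) = 0.110 with 50. Both exceed the planned maximum of 0.093.

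**The case against.** **The sign is right where the analysis is specified.** Protocol 6.1.1, SAP 2.1 and SAP 4.3.1 all speak of a reduction, and Protocol section 7 defers analysis detail to the SAP. This stands: a wrong result is unlikely in practice. The protocol sentence is still wrong as written for a primary endpoint.

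**The default table may not apply.** SAP 4.8 is generic and yields to the table descriptions in Appendix A, which is not in the supplied text. The template cells are also blank, so the *missing* row suggests a denominator without proving it. This stands, and it is why the denominator is called unsettled rather than wrong.

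**Little hangs on it.** There is no hypothesis test or success threshold, and SAP 4.1 reports the number of subjects available per visit, so a reader could work out either percentage. This lowers the stakes. The estimate is nevertheless the study's main result, and the SAP promises a robust one.

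**Stronger readings that the documents do not support.**
- A reader might infer that counting change values instead of subjects is itself a mismatch of unit. It is not: the folds are averaged, so each assessed subject has exactly one change value per visit, and the counts agree.
- A reader might infer from "All primary endpoint analyses will be also performed for the modITT and PP" that subjects without a Week 24 grade must be counted, since otherwise ITT and modITT would agree at Week 24. That is weak evidence. The same sentence covers the mean change, which without imputation is identical in the two sets at Week 24 whatever the responder denominator.
- A reader might take 90% against 60% as the expected effect. The documents give no dropout rate. Moreover, fewer than 60 may be enrolled when 40 have completed Week 24, so n = 40 need not mean 20 missing; if the ITT were also 40, the gap would be zero.

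**Conclusion.** The point holds in two limited parts.

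- **Sign.** Protocol 7.4.1 and the synopsis are wrong as written. Taken literally, they would turn 36/40 into 0/40 in the example. The same fault affects the 2-point threshold. The SAP's responder text needs no correction of direction.
- **Denominator.** The supplied text leaves the Week 24 responder denominator open, with provisions pointing both ways. The possible gap runs from 0 points with complete data, through 15.0 with 50 grades, to 30.0 with 40. The last is the extreme that the plan allows. These figures assume 60 in the ITT and 90% response among those graded, and the conclusion is subject to whatever Appendix A says.

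Both should be corrected. Neither undermines the design, and no formal decision depends on them.

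**What to change.** **Protocol 7.4.1 and synopsis.** Replace the rule with: *proportion of subjects with the NLF-SRS grade reduced by ≥1, or ≥2, points (change ≤ −1, or ≤ −2)*.

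**SAP 4.3.1, and the NLF-SRS responder proportions in 4.3.2 and 4.4.**
- Show n/N beside every percentage.
- Name subjects with a baseline grade and a grade at the visit concerned (Week 24 for the primary endpoint) as the primary denominator. This agrees with the SAP's precision statement and its no-imputation rule.
- Add, as a sensitivity figure, the percentage over all ITT subjects with a missing grade counted as not reduced.
- Say whether the *missing* row of the SAP 4.8 table enters the 100% for these endpoints.
- Qualify SAP 4.6 for the sensitivity figure and, because Protocol 7.3 also excludes imputation, list it in SAP section 6.

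If Appendix A already sets the denominator, move that rule into SAP 4.3.1.

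**Cost.** One corrected sentence in each of the two protocol places, a few sentences in the SAP, and one extra percentage per responder table. No new data are needed. The sensitivity figure will look less favourable than the primary one whenever grades are missing.

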7.4.2 Safety endpoints

AEs will be coded by the Medical Dictionary for Regulatory Activities (MedDRA) and listed by subject. Incidence of AEs will be summarised by preferred term (PT) and system organ class (SOC), and also by intensity, relationship to the investigational medical device or procedure, and seriousness.

8 Data management

8.1 Case report forms

A CRF will be completed for each subject enrolled in the investigation who received the investigational device.

A web-based standardized electronic CRF (eCRF) will be used to document the subjects' data during the course of the study. The eCRF is designed to accommodate the specific features of the study design. All data obtained after the subject has given informed consent must be recorded in the eCRF. The investigator will assure that all data are entered promptly, completely, and accurately according to the eCRF instructions, and conform to source documents. Data for all subjects screened for study have to be documented on a respective form (see Section 6.3.9) but no eCRF entry for screening/baseline failures will be made.

Only investigators and authorized designees are allowed to make entries in the eCRF. This will be regulated by appropriate reading and writing access. Completed eCRFs per visit, must be electronically signed by the investigator or authorized designee. Any change or addition will be recorded by an audit trail system.

The investigator or designee has to carefully answer queries issued by Data Management in the eCRF.

It is the investigators' obligation to assure documentation of all relevant data in the subject's file, such as medical history, concomitant diseases, date of study enrolment, visit dates, results of examinations, administrations of medication, and AEs.

8.2 Data management procedures

All data management activities will be conducted by the Sponsor's representative following their Standard Operating Procedures. The database will be built by the Sponsor's representative, and they will handle the data cleaning process, including logical check, medical checks, and query processes. Details on data handling will be described in the Data Management Plan. Computerized validation check programs on completeness, correctness, plausibility (such as range checks, cross-checks) will verify the data according to the Data Validation Plan. All identified discrepancies will be queried using DCFs and addressed to the investigator.

Regarding self-evident corrections (such as spelling and header corrections) if applicable, investigator's agreement will be obtained that these will be made by the Data Manager and documented in the audit trail.

The database will be soft locked when it is considered complete and accurate (i.e. all CRF pages entered, all data cleaning activities performed). The database will be hard locked after all the changes following the data review meeting have been performed and the database is considered complete and accurate. All changes will be tracked (audit trail). Sponsor approval prior to database hard lock is mandatory.

8.3 Data retention

The investigator shall retain all study records during the clinical investigation and for the period required by the applicable regulatory requirements, or for at least 15 years after the premature termination or completion of the clinical investigation, whichever is longer. However, the investigator should contact the Sponsor prior to destruction of any records or reports pertaining to the clinical investigation, in order to ensure they no longer need to be retained or in case of changes in between in the duration of the clinical documents archiving according to GCP. In addition, the Sponsor should be contacted if the investigator plans to leave the site, so that arrangements can be made for transfer of records.

The medical files of study participants must be retained in accordance with local legislation and in accordance with the maximum period of time permitted by the hospital, institution or private practice.

8.4 Report of the clinical investigation

Following completion of the clinical investigation, the results will be evaluated and the Clinical investigation report will be generated, including a summary of all available data, statistical measures, tabulated results, graphical results, and interpretations. A complete list of all adverse events will be enclosed. This report will be submitted to authorities as appropriate, within the timeframes defined per national regulation or by the EC.

9 Amendments to the clinical investigation plan

Any change to the CIP concerning the purpose of the study, the study design or the subject's eligibility can only be made in form of a written amendment to the CIP. Such amendments have to be discussed and signed by the Sponsor, the Coordinating Investigator, and the other investigators before implementation.

Amendments that might have an impact on study procedures to be performed and/or the well-being of the subjects require additional informed consent, which has to be given in writing by all subjects enrolled in the clinical investigation who are affected by the amendment.

10 Deviations from the clinical investigation plan

A CIP deviation is a failure to follow, intentionally or unintentionally, the requirements of the CIP. As required by national regulation or guidelines, requests for deviations and reports of deviations will be provided to the EC if the deviation affects subject's rights, safety and well-being, or the scientific integrity of the clinical investigation.

Under emergency circumstances, deviations from the CIP may proceed without prior approval by the Sponsor and favorable opinion of the EC if the rights, safety and well-being of human subjects need to be protected. Such deviations will be documented and reported to the Sponsor and the EC as soon as possible in accordance with national regulations.

All CIP deviations will be listed and their impact on evaluability of respective subjects will be discussed in a data review meeting prior to the hard data base lock.

11 Device accountability

Investigational device accountability is described in Section 6.2.7.

12 Statements of compliance

This clinical investigation will be conducted in compliance with the clinical investigation plan (CIP) and the following standards and regulatory requirements:

- International Standard ISO 14155:2011: Clinical investigation of medical devices for human subjects - Good clinical practice;
- Declaration of Helsinki, in its currently adopted version;
- Applicable sections of the national medical device law.

By acting in accordance with this CIP, the investigators and the study site personnel fulfil the requirements of the International Standard ISO 14155:2011.

The clinical investigation will not commence until a favourable opinion from the respective EC has been received. All additional requirements imposed by the EC will be followed.

A prior regulatory approval will also be sought, if required by national regulations.

Insurance coverage for damages emerging from the clinical investigation will be provided according to applicable legal requirements.

13 Informed consent process

Written informed consent must be obtained from each subject prior to initiation of any of the investigation-specific procedures.

The investigator or their authorized designee must give each subject complete and adequate verbal and written information about the investigation. The investigator must ensure that the subject is fully informed about the aims, procedures, potential risks, any discomforts, and expected benefits of the clinical investigation. Before consenting, the subject must be left with ample time to consider and ask questions. It must be emphasized that participation is voluntary and that the subject has the right to withdraw from the clinical investigation at any time without any justification and without prejudice. The subject must then sign and date the ICF prior to the conduct of any study procedures. The consent taker (investigator or study team member) must sign and date the ICF as well.

A copy of the Subject information Sheet and ICF will be given to the subjects for their records. The rights and welfare of the study participants will be protected by emphasizing to them that the quality of their medical care will not be adversely affected if they decline to participate in this clinical investigation or in case of withdrawal of their consent during the clinical investigation.

If amendments to the final CIP affect the subject's participation in the clinical investigation (e.g. a change in any procedure), the Subject information Sheet and the ICF must be updated to incorporate this modification, and the subject must sign the amended ICF indicating that they re-consent to participate in the clinical investigation.

14 Adverse events, adverse device effects and device deficiencies

